8.3.6.1. Pregnancy Testing

A serum pregnancy test will be required for all women of childbearing potential during screening and at the EOT visit; participants going into hospice are not required to provide EOT pregnancy test. Urine pregnancy tests will be performed locally on Day 1 of each cycle, as outlined in [Table 4](#), as medically indicated (eg, in case of loss of menstrual cycle, when pregnancy is suspected), or per country-specific requirement (note that country-required urine pregnancy testing will be outlined and communicated to investigational sites under separate cover). If a urine pregnancy test is positive, the results should be confirmed with a serum pregnancy test.

If the serum pregnancy test is negative after a urine test was positive, the investigator will assess the potential benefit/risk to the participant and determine whether it is in the participant's best interest to resume study drug and continue participation in the study.

If a pregnancy is confirmed by a serum pregnancy test, see Section [9.5](#) for reporting requirements.

8.3.6.2. Serology

Hepatitis screening assessments will be performed at the screening visit to assess infection and viral status; required analytes are shown in [Table 13](#). Generally, hepatitis tests should be performed early in the screening process due to the length of time needed to obtain the results. Additional tests may be performed if clinically indicated.

8.4. Pharmacokinetic Assessments

Pharmacokinetic parameters are not evaluated in this study.

[figure not shown]
8.5. Pharmacodynamic and Translational Assessments

Pharmacodynamic parameters are not evaluated in this study.

8.5.1. Tumor for Genomics Testing for FGFR Genetic Alterations and Gene Expression

All potential participants must be evaluated for FGFR mutations and rearrangements before enrollment. Participants with local lab data documenting an FGFR1, FGFR2, or FGFR3 mutation or translocation (in-frame fusion regardless of fusion partner) are eligible. Confirmatory testing through the central genomics laboratory will be performed on all participants (not required when tissue already profiled at the reference lab); results from the central laboratory are not required prior to enrollment. Details for sample collection, processing, and shipping will be provided in the Laboratory Manual.

[Appendix C](#) contains a list of the most common recurrent activating FGFR mutations (excluding the kinase domain) that have been previously described, are present in somatic mutation databases, and/or are homologous to activating mutations present in another FGFR. [Appendix C](#) is not all-inclusive, as extremely rare or novel activating alterations may not be present in the list.

8.5.2. Blood for Mutational and Other Correlative Analysis

[REDACTED] Analysis of tumor mutational status will be conducted by the sponsor or its designee, and other assays relevant to the objectives of the study may be performed based upon emerging data. Details for sample collection, processing, and shipping will be provided in the Laboratory Manual. The correlative analyses may include assessment of markers of immune and inflammation status, including cytokines and soluble receptors, as well as examination of markers associated with tumor metabolism. Other assays relevant to the objectives of the study may be performed based upon emerging data. [REDACTED]

Details for sample collection, processing, and shipping will be provided in the Laboratory Manual.

Blood or saliva will be collected at baseline for the purpose of tumor/normal matched sampling and assessment of germline versus somatic mutation status.

8.5.3. Tissue Biopsies

Tumor biopsies will be collected as specified below:

- **Screening:** Mandatory tumor tissue will be collected during screening. A fresh biopsy at screening is preferred; however, formalin-fixed paraffin embedded tissue is acceptable as long as the sample has been collected less than 12 months from date of screening (not required for participants who have already had tumor sequenced at the reference laboratory).

Note: Fresh tumor biopsies should be taken from nontarget lesions when possible.

- **Optional on-treatment:** An on-treatment biopsy may be collected during Cycle 2, between Day 7 and Day 14, but is allowed to be performed at any cycle; the on-treatment biopsy should be performed on a study drug administration day, preferably between Day 7 and Day 14.

Note: On-treatment biopsies should be taken from the same site as the screening biopsy whenever possible.

- **Optional end of treatment:** An EOT/at the time of progression biopsy is requested but not required from all participants. If EOT occurs less than 6 weeks after the on-treatment biopsy was performed, an EOT biopsy should not be performed.

8.6. Unscheduled Visits

Unscheduled visits may occur as clinically indicated. They can be used for visits that occur outside of visit windows and should be noted in the eCRF as an unscheduled visit.

8.7. End of Treatment

When the participant permanently discontinues study drug, whether the participant is terminating the study early or the participant has completed the study, the EOT visit should be conducted. If the EOT visit coincides with a regular study visit, the EOT evaluations will supersede those of

that scheduled visit, and the data should be entered in the EOT visit in the eCRF. The participant should be encouraged to return for the follow-up visit.

8.8. Follow-Up

8.8.1. Safety Follow-Up

The safety follow-up period is the interval between the EOT visit and the scheduled follow-up visit, which should occur 30 to 35 days after the EOT visit (or after the last dose of study treatment if the EOT visit was not performed). Adverse events and SAEs must be reported up until 1) at least 30 days after the last dose of study drug, the date of the follow-up visit, or the start of a new anticancer therapy or 2) until toxicities resolve, return to baseline, or are deemed irreversible, whichever is longer. Reasonable efforts should be made to have the participant return for the follow-up visit and report any AEs that may occur during this period. If the participant cannot return to the site for the safety follow-up visit (eg, lives far away), the participant should be contacted by telephone for assessment of AEs and SAEs. Sites should document this contact in the source.

If a participant is scheduled to begin a new anticancer therapy before the end of the 30- to 35-day safety follow-up period, the safety follow-up visit should be performed before new anticancer therapy is started. Once new anticancer therapy has been initiated, the participant will move into the survival follow-up period.

8.8.2. Post-Treatment Disease Follow-Up

Participants who discontinue study treatment for a reason other than disease progression will move into the disease status follow-up period and should be assessed every 9 weeks \pm 7 days by radiologic imaging to monitor disease status. Every effort should be made to collect information regarding disease status until:

- The start of new anticancer therapy: the start of the new treatment should be captured, but the participant should continue to have disease assessments until progressive disease.
- Disease progression (confirmed by a local radiologist).
- Death.
- The end of the study.

8.8.3. Survival Follow-Up

Once a participant has received the last dose of study treatment, confirmed disease progression, or starts a new anticancer therapy, the participant moves into the survival follow-up period and should be contacted by telephone, email, or visit at least every 12 weeks to assess for survival status until death, withdrawal of consent, or the end of the study, whichever occurs first.

For participants having entered the survival follow-up period of the study, the site will use continuing participant records to supply data on subsequent treatment regimens, tumor assessments (if discontinued treatment for a reason other than progression), and OS in the eCRF. For participants who do not intend to return to the study investigator for their ongoing care, follow-up should be maintained by phone contact, patient records, and public records/databases approximately every 12 weeks.

9. ADVERSE EVENTS: DEFINITIONS AND PROCEDURES FOR RECORDING, EVALUATING, FOLLOW-UP, AND REPORTING

9.1. Definition of Adverse Event

Adverse Event Definition

- An AE is any untoward medical occurrence associated with the use of a drug in humans, whether or not considered drug-related.
- An AE can therefore be any unfavorable and unintended sign (including an abnormal laboratory finding), symptom, or disease (new or exacerbated) temporally associated with the use of study treatment.

Events Meeting the Adverse Event Definition

- Any safety assessments (eg, ECG, vital signs measurements), including those that worsen from baseline, considered clinically significant in the medical and scientific judgment of the investigator (ie, not related to progression of underlying disease).
- Abnormal laboratory test results constitute an AE if they are considered clinically meaningful, induce clinical signs or symptoms, require concomitant therapy, or require changes in study drug. Whenever possible, a diagnosis (eg, anemia, thrombocytopenia) should be recorded in the eCRF rather than the abnormal lab result (eg, low hemoglobin, platelet count decreased).
- Exacerbation of a chronic or intermittent pre-existing condition including either an increase in frequency and/or intensity of the condition.
- New conditions detected or diagnosed after study treatment administration even though they may have been present before the start of the study.
- Signs, symptoms, or the clinical sequelae of a suspected drug-drug interaction.
- Signs, symptoms, or the clinical sequelae of a suspected overdose of either study treatment or a concomitant medication. Overdose per se will not be reported as an AE/SAE unless it is an intentional overdose taken with possible suicidal/self-harming intent. Such overdoses should be reported regardless of sequelae.

Events NOT Meeting the Adverse Event Definition

- Any clinically significant abnormal laboratory findings or other abnormal safety assessments that are associated with the underlying disease, unless judged by the investigator to be more severe than expected for the participant's condition.
- The disease/disorder being studied or expected progression, signs, or symptoms of the disease/disorder being studied, unless more severe than expected for the participant's condition or considered to be treatment-related by the investigator.
- Efficacy endpoints as outlined in Section 3 will not be reported as AE/SAEs, specifically, any event that is related to disease progression of the cancer under study. Unblinded aggregated efficacy endpoint events and safety data will be monitored to ensure the safety of the participants in the study. Any suspected endpoint that upon review is not progression of the cancer under study will be forwarded to Incyte Pharmacovigilance as a SAE within 24 hours of determination that the event is not progression of the cancer under study.
- Medical or surgical procedure (eg, endoscopy, appendectomy): the condition that leads to the procedure is the AE if it occurred after signing informed consent. If present before entering the study, the condition should be captured as medical history.
- Situations in which an untoward medical occurrence did not occur (social and/or convenience admission to a hospital).
- Anticipated day-to-day fluctuations of pre-existing disease(s) or condition(s) present or detected at the start of the study that do not worsen.

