8.3.1. Adverse Events

Adverse events will be monitored from the time the participant signs the ICF until at least 30-35 days after the last dose of study drug or until the start of new anticancer therapy, whichever occurs first. Adverse events that begin or worsen after informed consent should be recorded on the Adverse Events Form in the eCRF regardless of the assumption of a causal relationship with the study drug. Conditions that were already present at the time of informed consent should be recorded on the Medical History Form in the eCRF. Adverse events (including laboratory abnormalities that constitute AEs) should be described using a diagnosis whenever possible rather than by individual underlying signs and symptoms.

Adverse events will be reported by the participant (or, when appropriate, by a caregiver, surrogate, or the participant's legally authorized representative). The investigator and any qualified designees are responsible for detecting, documenting, and recording events that meet the definition of an AE or SAE and remain responsible for following-up on AEs that are serious, considered related to the study treatment/procedures, or that caused the participant to discontinue study drug. Care will be taken not to introduce bias when detecting AEs and/or SAEs.

Open-ended and nonleading verbal questioning of the participant, such as "How are you feeling?" is the preferred method to inquire about AE occurrences. Adverse events may also be detected when they are volunteered by the participant during the screening process or between visits, or through physical examinations, laboratory tests, or other assessments. The definition, reporting, and recording requirements for AEs are described in Section [9](#).

All SAEs will be recorded and reported to the sponsor or designee within 24 hours. The investigator will submit any updated SAE data to the sponsor within 24 hours of it being available.

After the initial AE/SAE report, the investigator is required to proactively follow each participant at subsequent visits/contacts. All SAEs will be followed until resolution, stabilization, the event is otherwise explained, or the participant is lost to follow-up (as defined in Section [7.3](#)).

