9.2. Definition of Serious Adverse Event

If an event is not an AE per definition above, then it cannot be an SAE even if serious conditions are met (eg, hospitalization for signs/symptoms of the disease under study, death due to progression of disease).

A Serious Adverse Event is defined as any untoward medical occurrence that, at any dose:

a. Results in death

b. Is life-threatening

The term 'life-threatening' in the definition of 'serious' refers to an adverse drug experience that places the participant, in the opinion of the initial reporter, at immediate risk of death from the adverse experience as it occurred. This does not include an adverse drug experience that, had it occurred in a more severe form, might have caused death.

c. Requires inpatient hospitalization or prolongation of existing hospitalization

In general, hospitalization signifies that the participant has been detained (usually involving at least an overnight stay) at the hospital or emergency ward for observation and/or treatment that would not have been appropriate in the physician's office or outpatient setting. Complications that occur during hospitalization are AEs. If a complication prolongs hospitalization or fulfills any other serious criteria, the event is serious. When in doubt as to whether "hospitalization" occurred or was necessary, the AE should be considered serious.

Hospitalization for elective treatment of a pre-existing condition that did not worsen from baseline is not considered an AE.

d. Results in persistent or significant disability/incapacity

- The term disability means a substantial disruption of a person's ability to conduct normal life functions.
- This definition is not intended to include experiences of relatively minor medical significance, such as uncomplicated headache, nausea, vomiting, diarrhea, influenza, and accidental trauma (eg, sprained ankle), that may interfere with or prevent everyday life functions but do not constitute a substantial disruption.

e. Is a congenital anomaly/birth defect

f. Other situations (Important Medical Event)

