9.4. Reporting of Serious Adverse Events

Regardless of suspected causality (eg, relationship to study drug or study procedure[s]), all SAEs occurring after the participant has signed the ICF through 30-35 days after the last dose of study treatment *or* until the participant starts a new anticancer therapy, whichever occurs earlier) must be reported to the sponsor (or designee) within **24 hours** of learning of its occurrence, unless otherwise specified by the Protocol. The investigator will submit any updated SAE data to the sponsor (or designee) within 24 hours of it being available.

Investigators are not obligated to actively seek AE or SAE information after conclusion of the study participation. However, if the investigator learns of any SAE, including a death, at any time after a participant has been discharged from the study, and he/she considers the event to be reasonably related to the study treatment or study participation, the investigator must notify the sponsor (or designee) within 24 hours of becoming aware of the event.

After the initial AE/SAE report, the investigator is required to proactively follow each participant at subsequent visits/contacts. All SAEs will be followed until resolution, stabilization, the event is otherwise explained, or the participant is lost to follow-up (as defined in Section [7.3](#)).

Prompt notification by the investigator to the sponsor of a SAE is essential so that legal obligations and ethical responsibilities towards the safety of participants and the safety of a study treatment under clinical investigation are met.

If the SAE is not documented in the [IB](#) for the study drug (new occurrence) and is thought to be related to the sponsor's study drug, the sponsor or its designee may urgently require further information from the investigator for reporting to health authorities. The sponsor or its designee may need to issue an Investigator Notification to inform all investigators involved in any study with the same drug that this SAE has been reported. Suspected Unexpected Serious Adverse Reactions will be collected and reported to the competent authorities and relevant ethics committees in accordance with Directive 2001/20/EC, or as per national regulatory requirements in participating countries.

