10.4.3. Safety Analyses

Safety analyses will be conducted for the safety population. Adverse events will be coded by the MedDRA dictionary, and TEAEs (ie, AEs reported for the first time or worsening of a pre-existing event after first dose of study drug/treatment) will be tabulated by preferred term and system organ class for all events, related events, and events of Grade 3 or higher.

Quantitative safety variables and their changes from baseline (eg, laboratory, vital signs) will be summarized with descriptive statistics. Clinically notable abnormal values will be flagged and tabulated based on predefined criteria.

The clinical laboratory data will be analyzed using summary statistics; no formal treatment group comparisons are planned. In addition, distributions of key laboratory parameters may be plotted over time; these values will also be classified into CTCAE toxicity grades, and tabulated.

Descriptive statistics and mean change from baseline will be determined for vital signs at each assessment time. Vital sign results will be reviewed for clinically notable abnormalities.

Descriptive statistics and mean change from baseline will be determined for each ECG parameter at each assessment time. Electrocardiogram results will be reviewed for clinically notable abnormalities according to predefined criteria (see Section 8.3.4). Participants exhibiting clinically notable ECG abnormalities will be listed.

Measures of exposure of study drug will be summarized by means of summary statistics.

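### Section 9.1 keeps unexpectedly severe or treatment-related progression events as AEs in one exclusion bullet and drops them without exception in the next

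*Protocol*

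**What the plan says.** Section 9.1 of the Protocol closes with a list of events that do not meet the AE definition. Two neighbouring bullets deal with progression.

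- **Disease bullet.** The disease under study, its expected progression, and its signs and symptoms are not AEs, "unless more severe than expected for the participant's condition or considered to be treatment-related by the investigator".
- **Endpoint bullet.** The efficacy endpoints of Section 3 "will not be reported as AE/SAEs, specifically, any event that is related to disease progression of the cancer under study". It then adds: "Any suspected endpoint that upon review is not progression of the cancer under study will be forwarded to Incyte Pharmacovigilance as a SAE", and sets the time as "within 24 hours of determination that the event is not progression of the cancer under study".

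Three other sections build on this list.

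- Section 9.2: "If an event is not an AE per definition above, then it cannot be an SAE even if serious conditions are met".
- Section 8.3.1: "All SAEs will be recorded and reported to the sponsor or designee within 24 hours". Section 9.4 covers "Regardless of suspected causality (eg, relationship to study drug or study procedure[s]), all SAEs occurring after the participant has signed the ICF" and counts the 24 hours from learning of the event, subject to anything the Protocol specifies otherwise.
- Section 10.4.3: TEAEs "will be tabulated by preferred term and system organ class for all events, related events, and events of Grade 3 or higher". Table 7 in Section 3 lists the occurrence of TEAEs and of treatment-related AEs among the secondary endpoints.

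**The concern.** Both bullets are current text in the same list, both cover events linked to progression, and nothing says which one prevails. A site that follows the disease bullet records a progression-related event it considers drug-related. A site that follows the endpoint bullet does not. The same clinical event can then appear in the safety tables at one centre and be absent at another.

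The events in dispute matter for the safety assessment: those judged related to study drug, and those worse than the disease would explain. An event dropped at the definition stage never becomes an SAE, does not enter expedited reporting, and is missing from the related-event and Grade 3 or higher tables. The trial has a single arm, so no comparison group would reveal the omission.

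A secondary point concerns timing. The endpoint bullet starts its 24 hours only when someone has determined that the event is not progression. It gives no time limit for that determination and does not say who makes it.

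**Working it through.** There is no stated figure to reproduce, and no arithmetic decides the point. The check is to apply each bullet to every kind of event that could be linked to progression.

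| Event | Disease bullet | Endpoint bullet | Result |
|---|---|---|---|
| (a) Expected progression, not considered treatment-related | Not an AE | Not reported | Agree |
| (b) Progression-related, more severe than expected | AE | Not reported | Conflict |
| (c) Progression-related, also considered treatment-related | AE | Not reported | Conflict |
| (d) Found on review not to be progression | Not excluded | Forwarded as an SAE | Agree |

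**Return path.** The route back in the endpoint bullet serves row (d) only. An event in row (b) or (c) is still related to progression after review, so it does not come back.

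**Neighbouring wording.** The bullet on abnormal laboratory findings and safety assessments, in the same list, also keeps findings that are more severe than expected. The endpoint bullet is the only one of the three without that exception.

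**Consequences.** Take an event in row (c) that meets a seriousness criterion.

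1. Under the disease bullet it is an AE, hence an SAE under Section 9.2. It is reportable within 24 hours under Sections 8.3.1 and 9.4, receives a causality assessment under Section 9.3, and is counted in the Section 10.4.3 tables.
2. Under the endpoint bullet it is not reported as an AE. By Section 9.2 it cannot then be an SAE, and each later step falls away.

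**Clock.** Take a serious event that may or may not be progression. Under Section 9.4 the 24 hours run from learning of it. Under the endpoint bullet they run from the determination that it is not progression. Section 9.4 gives way to other Protocol provisions, so the endpoint bullet can be read as the governing rule. On that reading the event has no fixed deadline while the determination is pending.

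**The case against.** The best reply is that the bullets have different subjects. The endpoint bullet speaks of efficacy endpoints, that is, formal progression and death, while the disease bullet speaks of progression with its signs and symptoms. A site facing a bleed that it judges drug-related would find a directly applicable rule in the disease bullet. An event attributed to the drug alone would fall outside the endpoint bullet altogether. This has some force and narrows the conflict, but does not remove it. The endpoint bullet extends to any event related to progression, which is wider than formal endpoints, and the Protocol states no limit. An event attributed to both drug and progression stays within it. The severity exception is not rescued by either reading.

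On the clock, the objection largely stands. A suspected endpoint has not yet been classed as an SAE, and Section 9.4 allows for a different rule. This is a gap in timing, not a direct contradiction.

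It can also be said that progression and death are still captured through PFS and OS, and that the endpoint bullet promises monitoring of aggregated endpoint and safety data. That is so, but neither puts the event into the related-AE tables or gives it a recorded causality assessment as an AE.

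Two stronger readings are tempting, and the documents do not support them.

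- A reader might infer that, because OS counts death of any cause, every death is exempt from SAE reporting. The sentence narrows itself to events related to progression, and the return path sends non-progression events to pharmacovigilance as SAEs.
- A reader might size the problem from Study INCB 54828-101 (Section 2.3.1). There, fatal SAEs in 11 of 106 monotherapy participants included 4 with disease progression and 1 malignant neoplasm progression. None of the fatal events was assessed as related to pemigatinib, and none is described as more severe than expected. On the information given, nothing places them in row (b) or (c). They show only that progression terms were recorded as SAEs in that study.

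**Conclusion.** The inconsistency is real and should be corrected. It is confined to progression-related events that are more severe than expected or also considered treatment-related. For expected, unrelated progression the two bullets give the same answer. There is one AE definition with two overlapping exclusions, only one of which carries the exception.

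The number of affected events cannot be computed from the documents. Counts of TEAEs, related AEs and SAEs may differ according to the bullet a site applies, by an unknown and possibly small amount. The ORR analysis is not touched.

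The conclusion rests on reading the endpoint bullet's reference to any progression-related event as written. If the sponsor meant formal endpoints only, the Protocol needs to say so. The timing point is secondary and rests on the Protocol's silence about how long the determination may take.

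**What to change.** 1. Make the endpoint bullet in Section 9.1 expressly subject to the exception in the disease bullet. Events related to progression would then be exempt from AE/SAE reporting except where they are more severe than expected or the investigator considers them treatment-related.
2. Reconcile the endpoint bullet's 24-hour clock with Sections 8.3.1 and 9.4, so that a serious event not yet determined to be progression has a defined deadline. One way is to count from awareness and reclassify by follow-up report. Another is to set a time limit on the determination and name who makes it.

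The cost is a Protocol wording change and a few initial SAE reports that are later reclassified as progression. Sample size, visits and the efficacy analysis are unaffected.
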